5.8 Exclusion criteria

- i. Known case of Primary skin disease associated with Itching.
- ii. Known case of liver disease.
- iii. Known case of iron deficiency anaemia ,hematological malignancy.
- iv. Known case of hypothyroidism & hyperthyroidism.
- v. Known case of allergic reaction to Opiates .
- vi. Pregnancy.
- vii. Drug abuse, or substance dependence.

5.9. Sample size: Sample size calculation for hypothesis testing of difference between two proportions:

$$n = \frac{p(100 - p) + q(100 - q)}{(p - q)^2} (z_{\alpha} + z_{\beta})^2$$

Where,

Z_{α} = Z value of standard normal distribution at a definite level of significance

Z_{β} = Z value of standard normal distribution at a definite level of power

p = Proportion of patients with expected outcome (response rate) in the experimental group

q = Proportion of patients with expected outcome (response rate) in the control group

Here,

Z_{α} = 1.96 at 95% Confidence Interval

Z_{β} = 1.63 at 95 % power

p = 64% (Fishbane et al., 2020b)

q = 29% (Fishbane et al., 2020b)

So,

$$n = \frac{64(100.0 - 64) + 29(100.0 - 29)}{(64 - 29)^2} (1.96 + 1.63)^2 \approx 46$$

Considering 10% lost to follow-up final sample will be

$$(46 + 46 \times 10\%) \approx 50.6 \approx 51$$

That means 51 patients in each group will be needed in each group to test the hypothesis.

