Baseline assessment: CKD patients in HD will be screened consecutively and prospectively by the above inclusion and exclusion criteria to select eligible patients. Eligible patients and their legal relatives will then fully explain the study protocol, their role in the study, and the risks of the study. They will be informed of their right to withdraw from the study at any stage. After getting written informed consent, they will be finally enrolled in the study. Detailed history clinical examination and relevant investigation will be done. Baseline demographic, clinical and biochemical information will be collected from the patients using the case record form and the scales. Blood samples will be collected after an overnight fasting period, with all aseptic precaution 5 mL of venous blood drawn into appropriate vacutainers. iPTH will be measured using a chemiluminescence immunoassay (CLIA). Serum calcium and phosphate will be analyzed using colorimetric methods on a Beckman Coulter AU480 or equivalent validated clinical chemistry analyzer.

Allocation: Once a participant is enrolled in the study and consents to participate, they will be assigned to a treatment group according to the randomization sequence. This assignment will be done immediately after the baseline assessment to ensure that it is truly random. Patients will be randomly assigned to either experimental group or placebo group with a 1:1 allocation. Randomization will be carried out using online software (Research Randomizer Version 4.0 at <https://www.randomizer.org>).

Blinding: The study will be conducted as a double-blind trial, meaning that both the participants and the investigators will be unaware of the treatment assignments.

Interventions:

In the experimental group:

Standard symptomatic treatment for itching + Difelikefalin Dose : 0.5 µg per kilogram of weight after each dialysis session.

Duration: 6 wks

In the control group:

Standard symptomatic treatment for itching + Placebo

Duration: 6 wks

Follow-up:

- i. At the end 3 wks by- WI-NRS scale, Skindex 10 scale & Adverse events
- ii. At the End of 6 wks: WI-NRS scale, Skindex 10 scale & Adverse events

During the 6-week intervention period, patients will report their worst itching intensity using the WI-NRS, and their quality of life will be assessed using the Skindex-10 questionnaire at prespecified follow-up intervals throughout the 6-week period.

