Appendix
Case record form

Protocol Title: “Effect of Difelikefalin on CKD-Associated Pruritus in Patients on Maintenance Hemodialysis: A Randomized, Placebo-Controlled Trial”

Patient’s identification			
1	Patient ID No.		
2	Patient name :		
3	Adress		
4	Contact no:		
5	Study group	Experimental=1 Control=2	
Demographic characteristics			
1	Age:years	
2	Sex:	0=Female 1=Male	
Clinical characteristics			
1	Duration of HDMonths/years	
2	Duration of pruritusMonths/years	
3	Etiology of CKD	1=HTN 2=DM 3=GN 4=Others	
4	Baseline use of antipruritic medication	Anti histamin- Others-	
5	Online Kt/V		
Biochemical			
1	Calcium(mmol/l)		
2	Phosphate(mmol/l)		
3	PTH(pg/ml)		

	Follow-up data	Baseline	At 3-wk	At 6-wk
1	WI-NRS score			
2	Skindex-10 scale total score			

	Adverse Effect		3 weeks	6weeks
1	Nausea	N0= 0 Yes= 1		
2	Vomiting	N0= 0 Yes= 1		
3	Dizziness	N0= 0 Yes= 1		
4	Abdominal pain	N0= 0 Yes= 1		
5	Muscle spasm	N0= 0 Yes= 1		
6	Fall	N0= 0 Yes= 1		
7	Withdrawal	N0= 0 Yes= 1		
8	Expired	N0= 0 Yes= 1		
9	Others	N0= 0 Yes= 1		

	Complete the study per the Protocol 0= No 1= yes
	If not reason for drop-out 1. Adverse experience 2. Failure to return for follow-up 3. Patients refuse treatment 4. Patient died 5. Non-co-operation 6. Insufficient therapeutic response

Signature of the researcher:

Signature of the Guide/Co-guide

A. Worst Itching Intensity Numerical Rating Scale

INSTRUCTIONS

Please indicate the intensity of the **WORST ITCHING** you experienced over the past 24 hours by marking the box with the number that best describes it. After completing the scale below, please provide your initials in the **SUBJECT INITIALS** box indicating that you completed the scale by yourself and the **DATE** and **TIME** you completed the scale.

Worst Itching Over the Past 24 Hours

Please indicate the intensity of the **WORST ITCHING** you experienced over the past 24 hours.

0	1	2	3	4	5	6	7	8	9	10
										
NO ITCHING					WORST ITCHING IMAGINABLE					

B. Skindex-10 Scale

INSTRUCTIONS: During the past WEEK , how often have you been bothered by:							
	0 (Never bothered)	1	2	3	4	5	6 (Always bothered)

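### The case record form merges stopping study drug with leaving the study, and section 5.12 does not secure week-3 and week-6 scores once the drug is stopped

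*Protocol*

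**What the plan says.** The study completion block of the case record form (Appendix) holds one status item: "Complete the study per the Protocol 0= No 1= yes". A 'no' leads to "If not reason for drop-out 1. Adverse experience 2. Failure to return for follow-up 3. Patients refuse treatment", and the list ends "4. Patient died 5. Non-co-operation 6. Insufficient therapeutic response". The form has no date of last dose and no code for a patient who is off drug but still followed. The adverse-effect table has a row headed Withdrawal, but does not say whether it means withdrawal from the drug or from the study.

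The outcome section of the same form has the columns "Follow-up data Baseline At 3-wk At 6-wk". Section 5.12, Follow-up, schedules the final assessment as "At the End of 6 wks: WI-NRS scale, Skindex 10 scale & Adverse events". Neither is conditional on still receiving study drug, and neither mentions patients who have stopped.

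On leaving, section 5.12 tells patients about one right only: "They will be informed of their right to withdraw from the study at any stage". Stopping treatment while staying in follow-up is not mentioned. The subject table in the Data and Safety Monitoring Plan offers active, completed or withdrawn as status, beside columns for adherence and intervention duration. Section 5.9 makes one allowance for attrition: "Considering 10% lost to follow-up final sample will be".

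**The concern.** Adverse experience, refusal of treatment and insufficient response are reasons to stop an injection. They do not make a patient unreachable. The study population is patients on maintenance haemodialysis in the department's own unit, so most who stop the drug should still attend and could still give a week-6 score. A form that calls them drop-outs invites staff to treat their participation as over.

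The scores at risk are not a random subset. Insufficient response is close to the outcome itself. Stopping for adverse events may be commoner on active drug: the Introduction describes adverse effects that rise with dose, but the protocol gives no stopping rates by arm, so this is an expectation only. If scores go missing for such reasons, the responder outcome, the mean change in WI-NRS and Skindex-10 are all affected.

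A statistical analysis plan can choose an analysis set and a rule for missing values, but it cannot recover a score that nobody collected. What is collected after stopping is fixed by the protocol and the form.

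**Working it through.** **1. Can the form record a patient who stops the drug but is seen at week 6?** The outcome columns can hold the score. The completion item cannot describe the patient. 'Yes' would misstate a course of treatment that the protocol sets at 6 weeks, and 'no' leads to a reason for drop-out. The monitoring table could show a short intervention duration with status 'completed', but it does not call for an outcome assessment.

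**2. The plan's own figures (section 5.9).** Inputs: response rates 64% and 29%, z-values 1.96 and 1.63.

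n = [64 × 36 + 29 × 71] / 35² × (1.96 + 1.63)² = 4363 / 1225 × 12.888 = 45.9, rounded to 46 per arm.

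46 × 1.10 = 50.6, rounded to 51 per arm. Both figures reproduce. So 51 − 46 = 5 patients per arm may be missing within the plan's own allowance.

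**3. What five missing patients per arm can do.** Apply the planned rates to the 46 observed: 0.64 × 46 = 29.4, taken as 29; 0.29 × 46 = 13.3, taken as 13.

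| Assumption about the 5 missing per arm | Active | Control | Difference |
|---|---|---|---|
| Left out | 29/46 (63.0%) | 13/46 (28.3%) | 34.8 points |
| All non-responders | 29/51 (56.9%) | 13/51 (25.5%) | 31.4 points |
| Active none, control all respond | 29/51 (56.9%) | 18/51 (35.3%) | 21.6 points |
| Active all, control none respond | 34/51 (66.7%) | 13/51 (25.5%) | 41.2 points |

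For 29/51 against 13/51, Pearson chi-square gives p of about 0.001. For the lowest bound, 29/51 against 18/51, Pearson p = 0.029, continuity-corrected p = 0.047 and Fisher p = 0.046.

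**4. Bias if only observed patients are analysed.** Suppose the true all-randomised rates are 64% and 29% (35 points), and a fraction d of each arm stops, is not scored, and consists of non-responders. The observed rate is then the true rate divided by (1 − d). The stopping fractions below are assumptions; the protocol gives none.

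| Stopping, active / control | Observed rates | Difference |
|---|---|---|
| 5% / 15% | 67.4% / 34.1% | 33.3 points |
| 10% / 10% | 71.1% / 32.2% | 38.9 points |
| 15% / 5% | 75.3% / 30.5% | 44.8 points |

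The shift runs from about −2 to +10 points. Its direction depends on which arm loses more patients.

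**The case against.** The strongest reply is that nothing in the protocol ends follow-up when the drug stops. The week-3 and week-6 assessments are scheduled for every patient, the form's columns are unconditional, and the completion block records a reason after the event without instructing anyone to stop assessing. All of this stands. A reader might infer from the drop-out list that the week-6 scores of drug stoppers are definitely lost; the documents do not support that.

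A reader might also infer that section 5.9 counts drug stoppers as lost to follow-up. It does not. It applies a 10% allowance without defining the term or referring to the form's categories.

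Third, the span of about 20 points between the extreme bounds might be read as avoidable uncertainty. It cannot be, because deaths, withdrawals of consent and true losses fall within the same 10%, and their share is not given. The lower bound also needs every missing control patient to be a responder, which sits badly with control patients stopping for lack of effect. If stoppers in both arms are non-responders, the figure is 31.4 points, close to the planned 35, and even the extreme bound stays below p = 0.05 on the tests shown.

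Finally, an unseen analysis plan may count stoppers as non-responders. That could settle the responder outcome by definition, but it would supply no WI-NRS or Skindex-10 value for the mean changes.

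What survives is narrower. The schedule is silent about patients who stop, while the form labels them drop-outs.

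**Conclusion.** The point holds as a defect in what the protocol and form arrange to collect. Stopping the drug and leaving the study share one code, and no sentence secures scores after stopping. Outcome-related missing data are therefore likely, though not certain, and intention to treat alone would not repair them.

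The size can only be illustrated. It rests on an assumed 5 of 51 missing per arm, the planned response rates among those observed and, for the 31.4-point figure, non-response in all the missing. How much of the loss would come from drug stopping, and in which arm, is not documented. The change should be made before data collection, because uncollected scores cannot be recovered later.

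**What to change.** In the case record form, replace the single completion item with two:

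- study drug stopped early, yes or no, with date of last dose and reason;
- left the study, yes or no, with date and reason.

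Keep all the present reasons available, including insufficient response and non-co-operation. A patient may truly leave for either, and removing them would hide informative data. Add matching columns to the monitoring plan's subject table.

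In section 5.12, Follow-up, add one sentence: WI-NRS, Skindex-10 and adverse events are collected at weeks 3 and 6 in every randomised patient, on or off study drug, unless the patient dies, withdraws consent for follow-up or cannot be traced.

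This changes only what is recorded, not when treatment is stopped. It costs one form block, two table columns and one sentence, and assessments can be made at routine dialysis sessions without extra visits. The downside is small: scores taken after stopping mix on-drug and off-drug experience, so the estimated effect may be slightly smaller.

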Appendix
